6.1. Study Procedures

- Candidates will review information about the study and complete a screening form.
- During the screening process, the candidate will be asked questions regarding their symptoms and medical history to ensure that they meet the requirements to participate in this study.
 Potential participants will also be asked questions to ensure that they do not meet any of the exclusion criteria and meet all of the inclusion criteria.
- After successful screening (participant does not meet any exclusion criteria), participants will review and sign study informed consent form.
- Upon verification of signed informed consent, participant will be enrolled into the study.
- At time of enrollment, participant will be given access to the HIPAA compliant study portal.
 - The study portal provides access to study information, signed informed consent form, instructions for test product use, frequently asked questions, study surveys, symptom diary, and data collection tools.
- Participant shall complete baseline assessments upon access to the portal.
 - Baseline assessment will include questions regarding the participants' demographics, medications, detailed information regarding their indigestion/heartburn including treatment.
- To ensure that baseline assessments are completed before test product is used by the
 participant, study materials and study welcome package will be shipped to the participant once
 the clinical study manager/clinical ops coordinator confirms that the baseline assessment has
 been completed.
- The welcome package will include an information sheet that will outline instructions for their participation in the trial, the test product, and paper forms of the documents (paper form of

- study documents will be provided for real time data collection, in the event that the participant cannot log into the study portal to input data).
- Once the participant receives the test product, the participant will log into the study portal to acknowledge the receipt of the test product.
- Study start date will be the reported date of receipt of test product.
- Participant will be sent weekly email reminders that remind them of their participation in the study.
- At the onset of the indigestion and heartburn episode, the participant will start a Symptom Diary and complete a 4-point Likert scale for each of the symptoms they are experiencing.
 - Onset is defined as the point in time the participant takes the test product for relief of symptoms.
- After completing the surveys, the participant will take the test product. The participant will take
 2 capsules per indigestion and heartburn episode. With a max of 6 capsules per day. (If
 participant takes 6 capsules in 1 day this will be defined as 3 indigestion and heartburn episodes
 and the participant will be exited from the study).
- After taking the test product, the participant will complete a 4-point Likert scale assessment for each symptom at 15 minutes, 30 minutes, and 1 hour after taking the test product.
- When the participants symptoms have resolved , the participant will complete the symptom diary.
- If the participant takes any other medication outside of the test product, the participant will record this on the symptom diary.
 - The participant is allowed to take alternative medications or supplements AFTER 1 hour from taking the test product.
- After taking the test product, the participant will be instructed to fill out an Adverse Event form for any side-effects experienced.
- After the first episode of indigestion and heartburn, the participant will be asked to complete the same process for another 2 episodes within the 60-day study time frame; however, these are not required.
- If the participant completes the required assessments for a total of 3 episodes of indigestion and heartburn, they will be prompted, by email, to exit the study.
- If the participant only completes the required assessments for the required 1 episode of indigestion and heartburn, the participant will be prompted, by email, to complete the study exit form and will be exited from the study on day 60 (60 days from the day of receipt of the test product).
- Neither the sponsor nor Hawthorne Effect Inc. will not collect any unused test product.
- Upon receipt of study exit survey and review of completed study forms, participant will receive an Amazon gift card of \$25 via email.

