- A longitudinal analysis will be performed for participants who report on more than one incident of heartburn or indigestion.
- Adverse events will be summarized.
- An additional data presentation will consist of results from both Treatment and Control
 in similar studies appearing in the literature. There will be no formal statistical
 comparison of results from this study and historical studies.
- The Net Promoter Score will be summarized and compared against outcomes.
- Comparison against normal behavior will use the paired sample t-test.

4. Study Design

The present study will be a single site, prospective, one arm observational study of minimal risk consisting of at least 200 participants who suffer from symptoms of occasional indigestion and heartburn. The participants must meet additional inclusion/exclusion criteria (see Inclusion/Exclusion Criteria). Participants will begin taking the capsules at the onset of indigestion and heartburn symptoms. Onset is defined as the point in time the participant takes the test product for relief of symptoms. When the participant decides to take the test product, they will report and rate their symptoms on a 4-point Likert scale in the symptom diary prior to taking the test product. After consuming the test product, the participant will complete a 4-point Likert scale for each symptom at 15 minutes, 30 minutes, and 1 hour after taking the test product. If needed the participant will be allowed to take an alternative medication an hour after taking the test product. If medication is taken, the participant will record this in their symptom diary.

Study enrollment and management will be decentralized, where participants do not visit an investigator or a clinic for clinical assessment. The participants will participate in the study at home. All data collected from during this study will be reported by the participant via eCRFs, eDiary, and other electronic data entries. If a visit is required, it will be conducted via remote contact by telephone.

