4.2. Required Behavior

During the hour directly following consumption of the test product, no medication or supplementation (including all CBD products) other than the test product should be taken

for relief of indigestion and heartburn symptoms. Once the 1-hour report has been recorded the participant may take other medications or supplements. If medication is taken, the participant will record this in their symptom diary.

Participants are asked to limit the consumption of alcohol beverages to less than or equal to two drinks per day.

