4.3. Participation Period

Participants are expected to participate in the study for 60 days after study start. The product may be used after each onset of indigestion and heartburn episode, but not exceeding three times per day. Participants will be discontinued from the study 60 days after Study Start or after three recorded episodes of indigestion and heartburn. Study start is defined as the day the participant recorded received receipt of the test product on the start form in the platform.

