13.1.2. Appendix B Instructions for Use

Instructions for Use Upset Stomach Relief

This test product was created for support with indigestion and heartburn, combining Deglycyrrhizinated licorice (DGL), Artichoke Leaf, Marshmallow Root, Ginger, and Chamomile for comprehensive, yet gentle plant-based support with indigestion. This formula is designed to promote digestion and feelings of digestive comfort, but also to help build long-term digestive wellness.

Daily Dosage:

2 capsules contain:

Active Ingredients: Licorice Extract, Artichoke Leaf Extract, Chamomile, Marshmallow Root, Ginger.

Inactive Ingredients: Capsule (Hydroxypropyl Methyl Cellulose, Purified Water, Carrageenan, Potassium Chloride), Rice Hull Concentrate.

Directions: Take 2 capsules at the onset of symptoms up to three times daily for relief of your indigestion and heartburn symptoms.

*These statements have not been evaluated by the Food and Drug Administration. This product is not intended to diagnose, treat, cure or prevent any disease.

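### Episodes are counted by doses, so re-dosing one unresolved episode (not intended by the plan, but neither barred nor flagged) is recorded as repeat incidents with new baselines

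*Combined protocol and SAP*

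**What the plan says.** Section 6.1 (Study Procedures) sets "2 capsules per indigestion and heartburn episode. With a max of 6 capsules per day". It adds that if a "participant takes 6 capsules in 1 day this will be defined as 3 indigestion and heartburn episodes", the participant is exited. A later item in the same section also prompts exit once the assessments for three episodes are complete.

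Section 4 (Study Design) defines the start of an episode: "Onset is defined as the point in time the participant takes the test product for relief of symptoms". Section 6.1 repeats this. At that point "they will report and rate their symptoms on a 4-point Likert scale in the symptom diary prior to taking the test product", and the schedule in Section 6.2 gives Events 2 and 3 their own rating at event start.

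On repeat use, Section 4.3 states: "The product may be used after each onset of indigestion and heartburn episode, but not exceeding three times per day". It ends participation at 60 days or "after three recorded episodes of indigestion and heartburn". Appendix B reads: "Take 2 capsules at the onset of symptoms up to three times daily for relief". Section 4.2 says that in the hour after a dose "no medication or supplementation (including all CBD products) other than the test product should be taken" for symptom relief, so it does not reach a second dose of the test product itself.

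No section asks for resolution, a symptom-free gap or a minimum interval before a new episode can start. The diary in Appendix E collects the time of onset, the time of dosing and the time of complete resolution (the last only where applicable), but no rule uses these times to separate episodes. Sections 7.1 and 7.3 send repeat incidents to a longitudinal analysis without a stated model. Section 7.2 expects more power if multiple incidents prove usable. The plan does not say which episode or episodes the primary analysis uses.

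**The concern.** Read together, these rules count doses and call them episodes. A person whose symptoms persist and who doses again acquires a second and perhaps a third incident. The onset score of each is simply the score at which the earlier dose left them. The baseline form makes this foreseeable: Appendix D offers more than two hours, and no resolution at all, as usual symptom durations.

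Re-dosing also depends on outcome. Those not relieved by the first dose have the most reason to take another, so any analysis that pools recorded incidents gives them extra weight. Three things are at stake: the longitudinal analysis, the extra power that Section 7.2 hopes for, and the primary analysis if it draws on more than the first recorded episode.

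**Working it through.** **1. The plan's own figure.** Section 7.2 gives a mean improvement of 0.5, SD 1.5, 90% power and 97 participants with a paired t-test. Alpha and sidedness are not stated, so two-sided 0.05 is assumed. The normal approximation gives (1.5 × (1.960 + 1.282) / 0.5)² ≈ 94.6, so 95. The noncentral t gives 97, with power 90.1%. The figure reproduces. It counts participants, not records, so the episode rule does not touch it.

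**2. One participant under the rule.** Take a single episode, scored before each of three doses and one hour after each.

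| Dose | Pre-dose | 60 min | Recorded as | Change |
|---|---|---|---|---|
| 1 | 2 | 2 | episode 1 | 0 |
| 2 | 2 | 2 | episode 2 | 0 |
| 3 | 2 | 0 | episode 3 | 2 |

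The records give a mean change of (0 + 0 + 2)/3 = 0.67, with one incident in three relieved within the hour. The one-hour change after the episode's first dose is 0. Scoring the late resolution against the first baseline with no fixed time point would give 2, and so would credit a dose that did nothing within its hour. The remedy must therefore fix the time point as well as the baseline.

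**3. Share of records.** The documents give no re-dosing rate. Assume that a fraction f of the 97 re-dose one episode three times and that all others give one record. The re-dosers' share of records is 3f / (1 + 2f).

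| f | Records | Share from re-dosers |
|---|---|---|
| 5% | 106.7 | 14% |
| 10% | 116.4 | 25% |
| 20% | 135.8 | 43% |
| 30% | 155.2 | 56% |

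**4. Direction.** Assume a first-dose mean of 0.5 over all participants, no first-dose change in re-dosers, and a mean change d after each re-dose. The mean over all records is (0.5 + 2fd) / (1 + 2f).

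| f | d = 0 | d = 0.5 | d = 1.0 |
|---|---|---|---|
| 10% | 0.42 | 0.50 | 0.58 |
| 20% | 0.36 | 0.50 | 0.64 |
| 30% | 0.31 | 0.50 | 0.69 |

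The pooled mean can fall below or rise above the first-dose mean, depending on the course after the re-dose.

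**5. The suggested power gain.** In the extreme case all 97 give three records, 291 in total. With within-participant correlation ICC, the effective number is 291 / (1 + 2 × ICC): 182, 146, 121, 104 and 97 for assumed ICC of 0.3, 0.5, 0.7, 0.9 and 1.0. A test that took the 291 as independent would have a true two-sided error of 12%, 17%, 21%, 24% and 26% instead of 5%. The plan does not say that independence will be assumed. The point applies to genuine repeats too, so it bounds what extra records can buy and does not measure the re-dosing effect.

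**The case against.** The plan plainly means one dose per episode. The sentence just before the six-capsule rule says so, Section 4.3 ties use to each onset, and unresolved symptoms have another route: alternative medication after the hour, noted in the diary. On this view the six-capsule sentence only multiplies out 3 × 2. Section 6.6 ships a three-episode supply, so a participant who has taken six capsules has none left, whatever the episodes are called. The longitudinal analysis is secondary and, under Section 7.1, hypothesis generating, and Section 7.3 leaves detail to a later analysis plan.

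Most of this stands. It makes re-dosing a departure that the plan fails to catch, not something the plan designs in. It does not remove the problem: a stated rule classifies the re-dosed episode as several, so the gap is more than detail still to come.

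A reader might infer four stronger things that the documents do not support:

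- That Sections 4.3 and 6.1 contradict each other. They agree on the daily maximum and on exit after three episodes.
- That the rule favours the product. Failed doses enter as zero changes too, and step 4 shows movement both ways.
- That time to other intervention is cut short at the next dose. No section defines that endpoint's origin or censoring, and the diary times allow it to be derived from the first dose.
- That the longitudinal analysis is mostly made up of such records. The frequency is unknown.

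**Conclusion.** The point holds as a defect of definition. Followed as written, the rules turn a re-dosed unresolved episode into two or three incidents with carried-over baselines. A second dose does so through the onset definition, and a third on the same day through the six-capsule rule. How much this matters depends on a rate the documents do not give. The 14% to 56% range is illustrative and assumes that every re-doser takes all three doses for one episode. The direction of bias cannot be stated in advance.

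The sample size is sound on this point. The primary analysis is exposed only if it uses more than the first episode, which the plan leaves open. The matter should be settled before the analysis plan is final, but it does not threaten the trial's main calculation.

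**What to change.** Change the analysis definitions only.

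- **Flag.** Using the diary's onset, dosing and resolution times, mark a dose as a re-dose within the same episode when the previous diary shows no resolution before it and both doses fall on the same day. Where the resolution field is blank, treat doses on different dates as separate episodes. Without that default, blank fields would merge truly separate episodes.
- **Scoring.** Score each episode at 15, 30 and 60 minutes after its first dose, against its first pre-dose rating.
- **Primary analysis.** Base it on the first dose of the first episode.
- **Longitudinal analysis.** Leave flagged re-doses out of the count of repeat incidents.
- **Time to other intervention.** Measure it from the episode's first dose.

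The cost is wording in the protocol and analysis plan, plus a derived flag. No new data are needed, and N = 97 stands. The downside is some same-day misclassification where resolution is blank; a sensitivity analysis that includes the flagged records will show its effect.

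Section 6.1 has two exit triggers, one by capsule count and one by completed assessments for three episodes. Their owners should reconcile both with the episode definition. No dosing or exit rule is proposed here.

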6.2. Study Schedule of Activities

Assessments	Screening	Consent	Before Receipt of Test Product	Test Product Received	Event 1	15 Minutes After Event Start	30 Minutes After Event Start	60 Minutes After Event Start
Study Window								
Screening Survey	X							
Consent		X						
Baseline Survey			X					
Demographics			X					
Acknowledgement of receipt of test product				X				
Symptom Diary					X			X
4-point Likert Scale					X	X	X	X
Test Product Consumed					X			
Medications & Supplements			X					
AE Assessment					X	X	X	X
Study Exit Survey								

Assessments	Event 2	15 Minutes After Event Start	30 Minutes After Event Start	60 Minutes After Event Start	Event 3	15 Minutes After Event Start	30 Minutes After Event Start	60 Minutes After Event Start	Study Exit
Study Window									
Screening Survey									
Consent									
Baseline Survey									
Demographics									
Acknowledgement of Receipt of Test Product									
Symptom Diary	X			X	X			X	
4-point Likert Scale	X	X	X	X	X	X	X	X	
Test Product Consumed	X				X				
Medications & Supplements									
AE Assessment	X	X	X	X	X	X	X	X	X
Study Exit Survey									X

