7.1. Study Outcomes Measures

Analysis populations:

The *intent to treat* (ITT) population consists of all participants who are consented, report the onset of indigestion and heartburn, and have taken the study medication at least once. The primary analysis will be in the ITT population.

Primary Endpoint:

The primary endpoint has two components, reduction in indigestion severity and reduction in heartburn severity. Participants will be asked to rate each symptom (bloating, early fullness during a meal, pain or discomfort in the upper abdomen, burning in the upper abdomen, pain/burning in the center of your chest, nausea, vomiting, burping) on a 4-point Likert scale at 4 time points: prior to taking the test product, 15, 30, and 60 minutes after taking the test product. The improvement in symptoms from baseline will be evaluated on a pairwise basis separately for each component and each time point. P-values will be computed for the improvement.

There is no control group for the primary analysis.

Secondary Endpoints:

Secondary endpoints will be gathered on the subjective experience of these participants related to general health, personal experience with the test product. The secondary endpoints will be self-reported by the participant on their online portal. There will be a questionnaire related to general health and the subjective experience of the participant administered at baseline and at study exit.

The purpose of the secondary analyses is to investigate the association between various baseline and other measurements and outcomes. These secondary analyses are considered hypothesis generating, and the descriptions are somewhat informal. The trial data may suggest secondary analyses not described here.

Secondary endpoints:

- The time to other intervention will be analyzed.
- A longitudinal analysis will be performed for participants who report on more than one incident of heartburn or indigestion.
- Adverse events will be summarized.
- An additional data presentation will consist of results from both Treatment and Control
 in similar studies appearing in the literature. There will be no formal statistical
 comparison of results from this study and historical studies.
- The Net Promoter Score will be summarized and compared against outcomes.
- Comparison against normal behavior will use the paired sample t-test.

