7.3. Analysis Plan

Separate tables will be presented showing the changes from baseline for each component and each time point. The changes will be evaluated by the paired sample t-test. A longitudinal analysis will be performed for participants who report on more than one incident of heartburn or indigestion.

General statistical methods:

Data will be analyzed using standard statistical methods, as further specified in a statistical analysis plan (SAP), which will be prepared in detail later.

- Data analysis will largely consist of summary statistics and graphs. The only formal group comparisons will be in covariate analyses.
- For continuous variables data presentation will consist of means, confidence intervals computed using the *t*-statistic, medians, and interquartile ranges. Group comparisons will use *t*-tests or ANOVA.
- For discrete variables confidence intervals will use the exact intervals, where available. Group comparisons will use Fisher's exact test, with the Monte Carlo version used where computationally necessary.
- For time to event variables analysis will use the Kaplan-Meier algorithm, and group comparisons will use the log-rank or proportional hazards methods, depending on the data type.
- Visual analog scale values will be treated as continuous variables. Frequency counts will also be provided for scales with 10 or fewer distinct response levels.
- Covariate analyses will investigate the relation between baseline and outcome variables, using methods appropriate to the data types involved. Age, gender, and baseline medications will be included in these analyses where appropriate data are available.
- Present intention is that the analysis will be performed in R, and the precise form of algorithms will be the default of R. Kaplan-Meier, log-rank, and proportional hazards algorithms will be the defaults of the survival package.

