Dain or Discomfort in the	Unner Abdemen				
Pain or Discomfort in the	Opper Abdomen	2	3		
No Symptom	Slight	Moderate	Severe		
Burning in the Upper Ab	domen				
0 No Symptom	1 Slight	2 Moderate	3 Severe		
Pain/Burning in the center	er of your chest				
0	1	2	3		
No Symptom	Slight	Moderate	Severe		
Nausea					
0	1	2	3		
No Symptom	Slight	Moderate	Severe		
Vomiting					
0	1	2	3		
No Symptom	Slight	Moderate	Severe		
Burping					
0	1	2	3		
No Symptom	Slight	Moderate	Severe		
Other:	1	2	3		
0 No Symptom	Slight	Moderate			
No Symptom	Stight	Woderate	Severe		
60 Minutes afte	er taking the	e test product			
Bloating					
0	1	2	3		
No Symptom	Slight	Moderate	Severe		

Early Fullness During a Meal 0 No Symptom	1 Slight	2 Moderate	3 Severe		
Pain or Discomfort in the Upp 0 No Symptom	oer Abdomen 1 Slight	2 Moderate	3 Severe		
Burning in the Upper Abdom 0 No Symptom	en 1 Slight	2 Moderate	3 Severe		
Pain/Burning in the center of 0 No Symptom	your chest 1 Slight	2 Moderate	3 Severe		
Nausea 0 No Symptom	1 Slight	2 Moderate	3 Severe		
Vomiting 0 No Symptom	1 Slight	2 Moderate	3 Severe		
Burping 0 No Symptom	1 Slight	2 Moderate	3 Severe		
Other: 0 No Symptom	1 Slight	2 Moderate	3 Severe		
After your symptoms resolveplease complete any of the following questions if applicable.					
Did your symptoms resolve completely with the test product? Yes No Time of complete symptom resolution:					

Did you need to take another medication	on: Yes N	No
Medication #1:	Dose:	Time:
Medication #2:	Dose:	Time:
Medication #3:	Dose:	Time:
Did your symptoms resolve completely	with taking your altern	native medication? Yes No
After taking the alternative medication,	, time of complete resol	lution of symptoms:

Did you experience any side effects after taking the test product? (Y/N) If yes, **Please fill out** the Adverse Event form.

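### No time is set for recording other remedies when an episode does not resolve, so time to other intervention may be under-recorded

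*Combined protocol and SAP*

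**What the plan says.** Section 7.1 lists the endpoint in one line: "The time to other intervention will be analyzed". Section 7.3 supplies the method: "For time to event variables analysis will use the Kaplan-Meier algorithm". Neither section states a time origin, an end of observation or a censoring rule. Section 7.1 also sets the status of the secondary analyses: "These secondary analyses are considered hypothesis generating, and the descriptions are somewhat informal".

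On recording, section 6.1 gives two adjacent instructions. One ties completion of the diary to resolution: "When the participants symptoms have resolved , the participant will complete the symptom diary". The next does not: "If the participant takes any other medication outside of the test product, the participant will record this on the symptom diary". Sections 4 and 4.2 repeat the unconditional instruction. On timing of use, section 6.1 says: "The participant is allowed to take alternative medications or supplements AFTER 1 hour from taking the test product".

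In Appendix E, the yes/no question on other medication and the drug, dose and time lines (room for three) stand in the last block, headed "After your symptoms resolveplease complete any of the following questions if applicable". The section 6.2 schedule marks the Symptom Diary at the start of each event and under "60 Minutes After Event Start", with no later column for that event. Its medications row is marked only before receipt of the product.

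**The concern.** A Kaplan-Meier analysis needs, for each episode, either a dated remedy or a known time up to which none was taken. Here the place for the date is reached through an event, resolution, that may not happen. The baseline form (Appendix D, items 4 and 5) itself offers non-resolution as a usual course, with or without medication. Participants whose symptoms persist are plausibly the likeliest to take something else, and they are the ones whom the diary heading does not call back.

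At stake are the remedy-free curve and any rate of other-remedy use taken from it. The Objectives say that the data may be used to design a two-arm trial. A remedy time that was never collected cannot be restored by a later analysis rule. The primary analysis is not touched: its ratings end at 60 minutes, before other remedies are permitted.

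**Working it through.** The plan gives no figure for this endpoint. Its one checkable design figure, 97 treated participants for 90% power, belongs to the primary paired t-test. It reproduces (mean 0.5, SD 1.5, two-sided 0.05 assumed: power 90.1%) but has no bearing here. The check is a comparison of passages, followed by illustrative arithmetic.

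**When can a remedy be recorded?**

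1. Permitted use starts after the 1-hour report (sections 4, 4.2 and 6.1).
2. The last scheduled diary mark is at 60 minutes (section 6.2), so it precedes permitted use.
3. Later completion is foreseen, but its trigger is resolution (section 6.1 and the Appendix E heading).
4. The instructions to record any other medication carry no condition, but also no time, and they lead to the same block.
5. Other contacts do not supply a time. Reminders are weekly and exit emails (6.1). A coordinator may prompt for forms (6.3). The 30-day contact is for participants who have sent no event information (6.5). Exit form item 6 asks only whether the product helped avoid alternative medication, yes or no, with no time and no episode.

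For an episode that resolves, the route works. For one that does not, no passage says when to answer.

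**How much could it matter?** The documents give neither a rate of remedy use nor a rate of non-recording, so both are assumed. Let *q* be true use and *u* the share of users who go unrecorded.

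- Blank counted as remedy-free: recorded use = *q*(1 − *u*).
- Blank dropped: recorded use = *q*(1 − *u*)/(1 − *qu*). Censoring at the 60-minute report gives the same proportion, because it removes the episode before any permitted remedy can occur.

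| *q* | *u* | Counted as remedy-free | Dropped |
|---|---|---|---|
| 30% | 10% | 0.30 × 0.90 = 27% | 0.27/0.97 = 27.8% |
| 30% | 25% | 0.30 × 0.75 = 22.5% | 0.225/0.925 = 24.3% |
| 30% | 50% | 0.30 × 0.50 = 15% | 0.15/0.85 = 17.6% |
| 20% | 25% | 0.20 × 0.75 = 15% | 0.15/0.95 = 15.8% |
| 40% | 25% | 0.40 × 0.75 = 30% | 0.30/0.90 = 33.3% |

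**Can the direction reverse?** Yes. Suppose that all users are recorded, but 10% of participants have unresolved episodes, take no remedy and return no closing block. If they are dropped, recorded use is 0.30/(1 − 0.10) = 33.3%, above the true 30%. With dropping, recorded use falls only if a larger share of users than of non-users goes missing. With blanks counted as remedy-free, missed users can only lower it.

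**The case against.** The strongest reply is that the plan already asks for this information. Three places tell participants to record any other medication, whether or not symptoms have resolved. The closing block has a No answer to whether symptoms resolved with the test product and another to whether they resolved with the alternative medication, so it was evidently meant to take failures. Coordinators may chase incomplete forms, and the gift card follows review of completed forms. The endpoint is exploratory, and censoring could still be set in the SAP that section 7.3 says will be prepared later.

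Much of this stands. A reader might infer that remedies are recorded only after resolution. The unconditional instructions and the No answers contradict that. A reader might also infer from the schedule that the diary closes at 60 minutes, so that almost no permitted remedy could be recorded. No passage closes it then; section 6.1 expects later completion, and Appendix E allows paper entry followed by online entry. A recorded rate near zero is therefore not a supported scenario.

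What the reply does not supply is a time. The No answers help a participant who opens the block, but the heading does not bring anyone to it while symptoms persist. A later SAP can define censoring, but it cannot supply remedy times that were not collected.

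**Conclusion.** The concern holds as an inconsistency in data collection with a real risk of under-ascertainment. Section 6.1, the Appendix E heading and the section 6.2 schedule give different timings, and none covers an episode that persists. The participants most plausibly missed are those with continuing symptoms.

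The size is unknown. Under the assumed 30% true use, recorded use runs from 27% down to 15% when 10% to 50% of users are missed and counted as remedy-free; it is 33% in the reverse case. It is tempting to conclude that the endpoint must favour the product. That is the likelier direction, since the closing questions are to be answered only where applicable and a blank could be read as no remedy. It is not established, because no rule for blank diaries is stated.

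The effect is confined to a hypothesis-generating secondary endpoint. The change is still worth making before data collection.

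**What to change.** Take the remedy questions (taken or not, what, when, and whether the episode has resolved) out of the block tied to resolution. Ask them for every episode at one fixed time after the 60-minute report, whether or not symptoms have resolved. Add that column to the section 6.2 schedule for Events 1 to 3, and reconcile section 6.1 and Appendix E with it. Name that time as the end of observation, and hence the censoring time, for time to other intervention, and state how an unanswered form is handled. None of this alters when other remedies may be taken.

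The cost is one new automated or coordinator prompt per episode, because the reminders now described are only weekly and exit emails. An automated prompt would also need a way to reach participants who first record an episode on paper. There is a little more participant burden and some recall error in remedy times.
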